Self-report smokeless tobacco cessation will be assessed at the end of treatment, 3 and 6-months post-intervention. **Self-report smokeless tobacco cessation at month 6 will be the primary outcome.**

Secondary outcomes, which will be subsequently evaluated as mediators of the intervention effects, will be assessed at baseline, end of treatment, and 3 and 6-months post-intervention.

Primary Outcome: Smokeless Tobacco Cessation Outcome. Self-reported abstinence from tobacco use will be collected at end of treatment, 3 and 6-months post-intervention. We will measure 7-day point prevalence abstinence by asking participants, "In the past 7 days, have you used smokeless tobacco (chew or dip)?" This binary outcome will be dichotomized as 0=no and 1=yes. We will also randomly select a 20% (10% in control and 10% in intervention arm) of those who report quitting at the end of treatment, 3 and 6 months to biochemically confirm cessation using saliva cotinine strips. NicAlert Semiquantitative test strips will be used and a 10 ng/ml cutoff will indicate exposure. Biochemically validated cessation at each of these assessment points will be coded as 0=no and 1=yes.

Mediator: Craving. We will assess craving using the Smokeless Tobacco Evaluation Questionnaire (STEQ) based on the Cigarette Evaluation Questionnaire (mCEQ) modified for ST users.⁴⁶ The STEQ is a 12-item scale assessing the degree to which participants experience the reinforcing effects of smokeless tobacco on a 7-point Likert scale. The scale has five domains: chewing satisfaction, psychological reward, enjoyment of sensations in cheek/gum, craving reduction, and aversion.

Mediator: Withdrawal. We will assess withdrawal using the self-report seven item Minnesota Nicotine Withdrawal Scale⁴⁷ as has been used in other smokeless tobacco cessation trials assessing withdrawal. This seven-item scale measures withdrawal symptoms (i.e., irritability, anxiety, difficulty concentrating, restlessness, increased appetite or weight gain, depression, and insomnia) and measured on an ordinal scale (0= not present) to 4 (severe). A total score ranging from 0 to 28 will be derived to measure severity of withdrawal symptoms, with higher total scores representing greater withdrawal. Internal consistency of the scales are reported to be between $\alpha= 0.76-0.91$.

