Mediator: Self-regulation. We will assess self-regulation using the Short-form Self-Regulation Questionnaire, which is a 31 item self-report survey measuring the ability to regulate behavior and achieve goals.⁴⁸ Participants indicate the extent to which they agree with each item using a 5-point Likert scale: 1 (Strongly Disagree), 2 (Somewhat Disagree), 3 (Neutral), 4 (Somewhat Agree), and 5 (Strongly Agree). The measure has a total scale computed by summing the items, with higher total scores indicating increased self-regulation. Internal consistency of the scale is reported to be $\alpha=0.92$.

Mediator: Restraint. We will measure restraint using a modified version of the Smoking Restraint Questionnaire⁴⁹ for smokeless tobacco by replacing all smoking references with smokeless tobacco. The Smoking Restraint Questionnaire is a four-item survey. The two binary questions of the questionnaire are scored 1 (No) and 5 (Yes). The two multiple-choice items are scored from 1 to 5. Total smokeless tobacco restraint is calculated as the sum of the four items. The minimum possible score is 4 and the maximum possible score is 20, with higher total scores indicating higher levels of restraint. Internal consistency of the scale is reported to be $\alpha=0.74$.

Sample Characteristics : Baseline sociodemographic and clinical measures will be collected to describe the characteristics of the total sample and intervention arms. Many of these measures are potential important moderators or mediators of intervention effects that will be explored after the specific aims are fully examined.

- **Demographics and Relevant Biological Variables.** We will assess age, sex, race, education, marital status, and socio-economic status (SES) at baseline using measures adapted from our prior research.
- **Smokeless and other Tobacco Use History.** At baseline, participants will be asked about their tobacco use habit including: number of chews/dips per day, number of quit attempts in the past year, age of chewing/dipping initiation and past use of other tobacco products including electronic cigarettes.
- **Nicotine Replacement Therapy (NRT) Use:** We will ask participants at all follow-up time points if they have used any NRT including the patch, gum or lozenge.

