A text-based reduction intervention for smokeless
tobacco cessation

NCT04315506

01/28/2022

Data Analysis Plan

We will use descriptive statistics to summarize the sample characteristics and study measures collected at baseline and longitudinally. We will perform non-directional statistical tests with the significance level set at 0.05 for all analyses. The primary outcome is self-report smokeless tobacco cessation at month 6 (Aims 1 & 3). Due to the exploratory nature of the mediator analyses, the significance level of 0.05 will not be adjusted for the multiple tests associated with steps for determining mediation (Aims 2 & 3). For the efficacy and mediator analyses we will perform, both intention-to-treat (ITT) and completers analyses. ITT analyses will be the primary analyses and will include all participants randomized to an intervention regardless of treatment or study completion. Completers analyses will include only those participants who complete the month 6 assessment, regardless of level of adherence to the SGR or control intervention. Effect sizes and 95% confidence intervals (CIs) will be reported to address clinical significance for the efficacy and mediator analyses. Analyses will be conducted by our faculty biostatistician [name] (Co-I) to ensure application of rigorous methods and implementation of quality assurance procedures. All data will be stored in REDCap at Duke University and downloaded to SAS Version 9.4 for the statistical analysis.

Handling of Missing Data. Missing smokeless tobacco cessation outcome data will be imputed as “did not quit” for the Aim 1 and 3 primary outcome analyses applying the ITT principle. Aim 2 will apply hierarchical mixed-effects trajectory models to assess change in withdrawal symptoms, craving, self-regulation and restraint. Trajectory methods will allow missing outcome data when estimating participant trajectories. To test the data missing at random (MAR) assumption of trajectory methods, intervention group differences in missing rate at each time point and number of missing values across time will be compared using tests for difference in proportion or cumulative counts. For missing covariate data in the models, imputation methods (e.g., multiple imputation) will be carefully applied as needed. The latter will be particularly important for the ITT analyses.

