will be evaluated separately (See **Figure 5**). First, the initial step of the formal mediation analysis will be to determine whether the intervention group significantly influences the trajectory of change in withdrawal symptoms, craving, self-regulation, and restraint (Path A). The Path A analysis will be completed in Aim 2. Second, logistic regression will be used to examine whether the slope coefficients for the individual trajectories of the proposed mediator are associated with cessation at 6 months (Path B). The final logistic regression model conducted for Aim 1 will be used to test for intervention group differences in cessation at 6 months post-intervention (Path C). Finally, the slope coefficients for the proposed mediator will be added as a covariate to the Path C logistic regression model (Path C'). The Path C' analysis will allow us to examine the effects of the intervention groups on Month 6 cessation after adjusting for the effects of change in the proposed mediator across time. For each proposed mediator of SGR effects, mediation will be established if the SGR group compared to the control group has significantly greater improvements in the mediator as an outcome (Path A), the degree of improvements in the mediator across time is related to cessation at 6 months (Path B), the SGR group has a significantly higher cessation rate at 6 months compared to the control group (Path C), and SGR effects on cessation are partially or fully diminished after adjusting for the mediator effect (Path C'). A Sobel's Test will be used to further determine the degree to which improvement in withdrawal, craving, self-regulation, and restraints mediate intervention effects. ORs and their 95% CIs will provide estimates of effect sizes.

Figure 5: Mediation Analysis Pathways

Statistical Power. The sample size of 500 (N=250 per intervention arm) will provide at least 90% power to address the primary aim (Aim 1), primary outcome (self-reported cessation at 6 months), and primary analysis (ITT analysis). A previous smokeless tobacco SGR study in smokeless tobacco resulted in a 27% cessation rate at 6-months.²⁵ Our pilot resulted in a 22% cessation rate at 6-months. Given the improvements to our

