SGR intervention, we conservatively estimate a slightly higher quit rate at 25% at 6-months. The Enough Snuff Control intervention has yielded quit rates between 16-18% at 6-months;^{43,44} however, these studies were clinic-based and deployed out of dental offices with military personnel, representing a different population and mode of delivery than we are proposing. A similar, web-based version of the intervention delivered remotely yielded quit rates of 12%.³⁰ Given the low-touch remote nature of our study and the focus on rural and underserved populations, we expect quit rates in the control group to be closer to 12% at 6-months. Therefore, we estimate a medium effect at 6-months. In summary, the target sample size is based on the assumptions that: (1) logistic regression will be performed with two-tailed significance set at 0.05; and (2) the quit rate at month-6 may be as low as 25% in the SGR group and 12% in the control group at 6-months for the ITT analysis (odds ratio of 2.44, Cohen's *d* equivalent of 0.493, approximate medium effect); Consistent with prior smokeless intervention studies, the target sample size will not be adjusted for attrition rate and dropouts will be coded as continued to use. Based on these assumptions, a sample size of 250 per arm will provide 96% power to test the primary aim. If an attrition rate of 30%

is observed in each arm of the proposed study, the resulting sample size of 175 per arm will provide at least 80% power for the completers analysis for Aim 1.

Addressing scientific rigor and reproducibility. All final study procedures will be documented in detail with accompanying scripts, documents, examples and measures. Our assessments and reports will include descriptive statistics. The study PI will oversee the training of study staff and make sure all procedures meet high standards of fidelity using a checklist of key tasks with periodic observations of performance of tasks. Facebook recruitment quality control will be maintained by [name] with consultation from [name]. Texting quality control standards will be maintained under the supervision of [name]. [name] will oversee quality control of all assessment measures during the study. Further, the study statistician, [name], will document data quality control standards and procedures (e.g., data checking).

Potential Risks and Challenges

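### Exploratory Aim 3 relates quitting to each mediator's slope without the participant's baseline score on that mediator, so real mediation could be missed

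*SAP*

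**What the plan says.** The SAP (Exploratory Aim 3 Statistical Analysis) takes each participant's mediator slope from the Aim 2 random-coefficients model. For Path B, "logistic regression will be used to examine whether the slope coefficients for the individual trajectories of the proposed mediator are associated with cessation at 6", meaning month 6. For Path C', "the slope coefficients for the proposed mediator will be added as a covariate to the Path C logistic regression model", where Path C is the final Aim 1 model. The baseline mediator score is named in neither step, and Path B names no covariates at all.

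The score is available. The Protocol (Measures, Outcomes and Mediators) says the mediators "will be assessed at baseline, end of treatment, and 3 and 6-months post-intervention". The scales are bounded. For withdrawal, "A total score ranging from 0 to 28 will be derived to measure severity of withdrawal symptoms", with higher scores worse. For restraint, "The minimum possible score is 4 and the maximum possible score is 20", with higher scores better. The item formats bound the other two: craving has 12 seven-point items, and self-regulation has 31 items scored 1 to 5, so a sum between 31 and 155.

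The SAP (Sample Characteristics) lets baseline variables into the efficacy and mediation models through tests of arm difference, and drops non-significant covariates from the final models.

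**The concern.** A slope is a change measure whose first point is the baseline score. On a bounded scale, a participant who starts near the favourable end has little room to improve. For withdrawal and craving that is the low starter. For restraint and self-regulation it is the high starter. Starting level and amount of improvement may therefore be negatively correlated. If starting level also predicts quitting, participants who began well quit more often but show flat slopes, while those who began badly improve steeply but quit less often. The slope coefficient then mixes the effect of improving with the effect of where the person began.

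Randomization does not remove this, because the slope is not randomized. Paths B and C' are two of the four conditions for declaring mediation, and the Sobel test depends on the same coefficient. The Protocol wants the mechanism results to identify intervention targets, so a working mediator that appears unrelated to quitting would mislead.

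**Working it through.** **The plan's own figure.** The only power statement is for Aim 1: "The sample size of 500 (N=250 per intervention arm) will provide at least 90% power", with a quit rate that "the quit rate at month-6 may be as low as 25% in the SGR group and 12% in the control group at 6-months". For two proportions at two-sided 0.05, the pooled rate is 0.185, so:

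- SE under no difference = sqrt(2 × 0.185 × 0.815 / 250) = 0.0347.
- SE under the alternative = sqrt((0.25 × 0.75 + 0.12 × 0.88) / 250) = 0.0342.
- (0.13 − 1.96 × 0.0347) / 0.0342 = 1.81, which gives power 96.5%.

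The SAP's 96% is reproduced, and this point does not change it. There is no power figure for Aim 3.

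**Does the covariate screen cover the gap?** It tests arm imbalance. Under randomization, a given mediator's baseline score is flagged in about 5% of trials. At least one of four is flagged in 1 − 0.95^4 = 18.5% if the four are independent. Neither event relates to confounding between mediator and outcome.

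**Size of the bias.** Take unit SDs for starting level and slope, correlation ρ, and log-odds effects b_level and b_change on quitting. Leaving baseline out gives a slope coefficient of approximately b_change + ρ × b_level. With both effects assumed to be −0.30 (a withdrawal-type scale):

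- ρ = 0: −0.30.
- ρ = −0.3: −0.30 + 0.09 = −0.21.
- ρ = −0.5: −0.30 + 0.15 = −0.15.

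**Simulation.** From the documents: 250 per arm, four visits (0, 1.5, 4.5 and 7.5 months), and the test level ("We will perform non-directional statistical tests with the significance level set at 0.05 for all analyses"). Assumed: residual variance 0.5, arm effect on slope −0.35 SD, direct arm effect 0.6 on the log-odds scale, intercept −2, complete data. Individual slopes are shrunken estimates from the random-coefficients model, and arm is in the logistic model. Ranges span separate runs.

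| Scenario | Correlation | Slope term significant, without baseline | With baseline |
|---|---|---|---|
| Level and change both matter | 0 | about 65-67% | about 65-67% |
| | −0.3 | 30-33% | 53-55% |
| | −0.5 | 13-15% | 38-39% |
| Only level matters | 0 | 7% | 7% |
| | −0.3 | 5.5% | 5.6% |
| | −0.5 | 14-17% | 5% |
| Only change matters | 0 | 47% | 47% |
| | −0.3 | 45% | 41% |
| | −0.5 | 44% | 31-33% |

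With both effects present and ρ = −0.5, the mean coefficient is −0.14 without baseline, close to the −0.15 above, and −0.33 with it.

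**Bounded-scale check.** The simulation above imposes the correlation. A second one clips scores to 0-28 and lets the correlation arise. It assumes a true change effect of 0.15 per point in log-odds and a control quit rate of 12%.

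- Baseline mean 8, SD 6 (near the floor): the slope-baseline correlation is about −0.28. With a baseline effect of 0.10 per point, the Path C' slope coefficient is −0.09 without baseline and −0.20 with it, and Sobel power is 25% versus 72%. With a baseline effect of 0.15, the coefficients are −0.05 and −0.21, and Sobel power is 10% versus 75%.
- Baseline mean 14, SD 5 (away from the floor): Sobel power is 82% versus 88% (effect 0.10) and 83% versus 92% (effect 0.15).
- No baseline effect on quitting: Sobel power is 66% versus 60% near the floor and 75% versus 75% away from it.

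The adjusted coefficients of −0.20 and −0.21 exceed the generating 0.15 in size. Adjusting for a single baseline score measured with error reduces the confounding but does not remove it exactly, so these Sobel gains should not be read as pure recovery of signal.

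**The case against.** The strongest reply is that both conditions are unproven. No document figure shows any mediator starting near a bound. The Protocol (Significance) calls withdrawal symptoms an important determinant of success, but it is speaking of managing them during a quit attempt, not of baseline scores in daily users. The predictor it names is nicotine dependence, which is a separate measure. Without a link from starting level to quitting there is no distortion. All of this stands, so the size can only be shown as a range.

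A reader might also infer that the plan could declare mediation falsely, because a slope whose change does nothing can become significant at strong correlation. The SAP's own rule does not support that reading. The spurious coefficient has the wrong sign: by the formula above, 0 + (−0.5)(−0.30) = +0.15. Adjusting for it enlarges the SGR effect, so the requirement that Path C' diminish the effect fails. At −0.5, only about 0.1-0.2% of simulated trials met all the direction-consistent conditions. At −0.3 there was no inflation at all.

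Nor is the baseline score excluded absolutely: Path C' extends the final Aim 1 model, which could contain it after a chance imbalance. That route is real but weak. Finally, if only change matters, which is Aim 3's own hypothesis, adjustment costs power. That cost is accepted below.

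**Conclusion.** The omission is real, and its likely consequence is missed mediation rather than false mediation. It matters only if starting level both limits the slope and predicts quitting; both are assumptions. Under them, the loss of slope power ranges from nothing at zero correlation to roughly 22 points at −0.3 and 24-25 points at −0.5. On a bounded scale, the loss is large near the bound and modest away from it. Aim 1 and the randomized Path A comparison are unaffected. Because Aim 3 is labelled exploratory, this is a cheap improvement of low severity.

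**What to change.** In the SAP's Exploratory Aim 3 section, prespecify that the participant's baseline score on the same mediator enters the Path B and Path C' logistic models together with intervention group, whatever the baseline arm comparisons show and without significance screening. Add the same score to a version of Path C used only for comparison with Path C', so that the two models differ only by the slope. The Aim 1 model itself stays as it is. Keep the slope-only models as a sensitivity analysis.

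The cost is one sentence, no new data, one extra parameter per model, and a separate comparison Path C for each mediator. If starting level does not predict quitting, slope power falls by about 0, 4 and 11-13 points at correlations 0, −0.3 and −0.5.

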Aim 2 Statistical Analysis. We will use hierarchical mixed-effects models for repeated measures with *a posteriori* contrasts at each time point to test for intervention group differences in the trajectory of changes in severity of craving, withdrawal, self-regulation, and restraints across time (baseline, end of treatment, 3 and 6 months post-intervention). Specifically, random coefficients regression model (RRM) for longitudinal data will be used to compare the rate and pattern of change of these outcomes across time. Fixed effects will be intervention group, time, and group-by-time, while random effects will be participant and participant-by-time. A covariate-adjusted analysis will also be conducted to evaluate the influence of baseline covariates and biological variables (e.g., age and sex effects and their interactions with group). The model will be fitted for significant non-linear change within one or both intervention groups. Intraclass coefficients across time along with Cohen *d* equivalents and their 95% CIs at each time point will be used to address intervention effect sizes.

Exploratory Aim 3 Statistical Analysis. We will conduct mediator analyses using criteria recommended by Baron and Kenny⁵² as well as analytic guidelines from Kraemer et al.⁵¹ to explore whether changes in withdrawal symptoms, craving, self-regulation, and restraint mediate intervention group effects on tobacco use cessation across the 6-months. Each proposed mediator

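### Path B of the mediation rule is specified without intervention arm, so a mediator that does nothing within either arm can be declared established

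*SAP*

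**What the plan says.** All of this is in the SAP. The Aim 2 Statistical Analysis fits a random-coefficients model to each mediator: "Fixed effects will be intervention group, time, and group-by-time, while random effects will be participant and participant-by-time". The group-by-time term lets trajectories differ systematically by arm.

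The Exploratory Aim 3 Statistical Analysis then sets out four steps for each of four mediators (withdrawal, craving, self-regulation, restraint), taken one at a time:

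- **Path A:** arm affects the mediator trajectory (from Aim 2).
- **Path B:** a logistic regression asks whether "the slope coefficients for the individual trajectories of the proposed mediator are associated with cessation at 6 months (Path B"). No other term is named.
- **Path C:** arm affects month-6 cessation (the final Aim 1 model).
- **Path C':** "the slope coefficients for the proposed mediator will be added as a covariate to the Path C logistic regression model (Path C"'). The stated use of this model is the adjusted arm effect.

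Mediation is to be treated as established when four conditions hold. The Path B condition is that "the degree of improvements in the mediator across time is related to cessation at 6 months (Path B"), with no requirement that this hold given arm. The Path C' condition is that "SGR effects on cessation are partially or fully diminished after adjusting for the mediator effect (Path C"'), with no size, test or interval attached.

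A further sentence adds: "A Sobel's Test will be used to further determine the degree to which improvement in withdrawal, craving, self-regulation, and restraints mediate intervention effects". This is not one of the four conditions, and the SAP does not say which mediator coefficient enters it.

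**The concern.** A mediator must be related to the outcome among participants in the same arm. A pooled regression of cessation on slope does not test that. When SGR moves the mediator (Path A) and raises quitting (Path C), SGR participants have both better slopes and more quits. The pooled sample then shows an association even if slope and quitting are unrelated within each arm.

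Aim 3 is meant to tell two situations apart: SGR works through restraint, say, or SGR changes restraint and separately helps people quit. The rule as written can report the second as the first. The Protocol (Significance, Summary; Innovation) says the mechanism findings should guide intervention targets and later treatment strategies, so a false mechanism would carry forward.

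**Working it through.** **Inputs from the SAP (Statistical Power and opening paragraph).** 250 per arm; quit rates 25% and 12%; two-sided 0.05; 30% attrition leaves 175 per arm for completers.

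**Input not in the documents.** The arm difference in mediator slope, *d*, in SDs of individual slopes. It is assumed and varied from 0 to 1.5.

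**Step 1: reproduce the plan's power (the Path C test).** With mean rate 0.185,

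z = [0.13·√250 − 1.96·√(2·0.185·0.815)] / √(0.25·0.75 + 0.12·0.88) = (2.055 − 1.076)/0.541 = 1.81,

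so power is 96.5%, against 96% stated. The odds ratio is (0.25/0.75)/(0.12/0.88) = 2.44, and ln(2.444)·√3/π = 0.493, both as stated. Path C will therefore nearly always be met if the plan's assumptions hold.

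**Step 2: hand check of Path B for a null mediator.** Let slope be N(*d*·arm, 1), with no effect on quitting within arm.

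- Expected quitters: 62.5 + 30 = 92.5. Expected non-quitters: 187.5 + 220 = 407.5.
- SGR share: 62.5/92.5 = 0.676 among quitters and 187.5/407.5 = 0.460 among non-quitters.
- The mean slope therefore differs between quitters and non-quitters by 0.216·*d*, purely through arm.
- At *d* = 0.5 the difference is 0.108. The variances are 1 + 0.25·0.676·0.324 = 1.055 and 1 + 0.25·0.460·0.540 = 1.062. The SE is √(1.055/92.5 + 1.062/407.5) = 0.118.
- z = 0.108/0.118 = 0.91. The chance of |Z| > 1.96 is about 0.147 + 0.002 = 14.9%, where a null mediator should give 5%.

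**Step 3: simulation of the whole rule.** 4,000 trials per scenario under the same null mediator. Logistic models fitted: cessation on slope (B), on arm (C), and on arm plus slope (C'). The rule counts as met when A, B and C are significant in the favourable direction and the arm coefficient is smaller in C' than in C.

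| *d* (SD) | Path B significant, no arm term | Path B significant, arm included | Rule met, as written | Rule met, arm in Path B |
|---|---|---|---|---|
| 0 | 4.8% | 4.7% | 0.2% | 0.1% |
| 0.2 | 6.8% | 5.0% | 4.3% | 1.6% |
| 0.3 | 8.5% | 5.1% | 7.4% | 2.2% |
| 0.5 | 15.2% | 5.0% | 14.8% | 2.5% |
| 0.8 | 27.9% | 5.1% | 27.0% | 2.2% |
| 1.0 | 38.0% | 4.3% | 34.6% | 1.9% |
| 1.5 | 61.2% | 4.7% | 44.0% | 2.4% |

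The 15.2% at *d* = 0.5 agrees with the hand check. At 175 per arm the rule is met in 10.9% (*d* = 0.5) and 26.8% (*d* = 1.0), against 2.2% and 2.3% with arm in Path B.

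**Step 4: source of the excess.** At *d* = 0, Path B without arm rejects 4.8%. With *d* = 0.5 but quit rates of 12% in both arms, it rejects 5.3%. Both are nominal, so the excess needs arm to drive slope and cessation together.

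**Step 5: do the other criteria protect?** At *d* = 0.5, Path A is met in essentially all trials and Path C in 96.4%. The arm effect shrinks numerically in C' in 51.2%. That half does not filter Path B: the rule is met in 14.8% of trials and Path B is significant in 15.2%, so almost every false Path B passes. A chance positive slope coefficient helps meet both conditions.

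**The case against.** **Arm is not expressly excluded.** The SAP lists no covariates for Path B but does not say there are none, whereas Aim 1 does say its first model has no covariates. It also cites mediation frameworks ("We will conduct mediator analyses using criteria recommended by Baron and Kenny"), and the pathway figure is not available here. This is fair as far as it goes. But the joint model is described as a separate, later step, and the decision rule repeats Path B without conditioning on arm. Omission is the natural reading.

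**The slopes might be random-effect deviations with the group-by-time effect removed.** The confounding would then largely vanish. But such slopes would carry no arm difference, and adding them in Path C' could not show how much of the arm effect the mediator explains. Total individual slopes are the reading that makes the plan coherent.

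**The size depends on how the Path C' condition is read.** The simulation counts any reduction, which is the literal meaning of a partial one. Requiring at least a 10% fall in the arm log-odds ratio gives 0.3%, 1.1%, 5.2% and 13.5% at 0.2, 0.3, 0.5 and 0.8 SD. Requiring the arm effect to lose significance gives at most 1.6% up to 0.8 SD. This stands as a caution on magnitude. The SAP sets neither threshold.

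**The Sobel test could rescue the rule.** Added as a requirement with the arm-adjusted coefficient, it brings the rate to 1.6% at 0.5 SD. With the unadjusted Path B coefficient the rate is still 11.9%. The SAP neither requires the test nor names the coefficient.

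**Aim 3 is exploratory.** This limits the severity: the primary analysis, sample size and conduct are untouched, and the correct coefficient will appear in the C' output. It does not make the stated rule valid.

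**Conclusion.** The concern holds: the Path B criterion is wrong as written. Under the plan's own sample size and quit rates, a mediator with no within-arm effect is declared established in 14.8% of trials at an arm difference of 0.5 SD, and in 7.4% to 27.0% across 0.3 to 0.8 SD. With arm in Path B the rate is at most 2.5%. These are rates per mediator, and four are tested without multiplicity adjustment.

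The figures rest on three assumptions: *d*, which the documents do not give; total individual slopes, measured without error; and any numerical reduction satisfying Path C'. The problem is small at 0.2 SD or below, and smaller under a stricter Path C' condition. It should be corrected, but it does not affect the primary result.

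**What to change.** In the Exploratory Aim 3 section, define Path B as the mediator-slope coefficient, with its test, in the logistic model containing both arm and slope. Reword the criterion so that the mediator slope must be associated with cessation after adjustment for intervention arm. State that the Sobel test uses this same coefficient. It would also help to say that the slopes are total individual slopes, and to judge mediation on the indirect effect and its confidence interval, so that the undefined reduction in Path C' no longer carries weight.

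The core change is one sentence. The model is already planned as Path C', and no new data or change in sample size is needed.
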